Other safety evaluations will include assessment of adverse events, physical examinations, 12-lead ECGs, vital signs (including temperature, respiratory rate, and seated blood pressure and pulse), clinical chemistry laboratory evaluations, additional laboratory evaluations including prothrombin time/international normalized ratio (PT/INR), activated partial thromboplastin time (aPTT), hematology panel, urinalysis, and pregnancy test (female patients of child bearing potential only).

Statistical Methods:

Demographic and other patient data will be summarized by treatment group using descriptive statistics.

The primary efficacy comparison will compare the SelK2 only-treated, SelK2 and enoxaparin-treated, and enoxaparin only-treated arms. The difference in the total VTE rate determined during the entire Treatment Phase will be estimated. The 1-sided lower 90% CI of the difference between the SelK2 and enoxaparin groups only arms as well as the difference between the adaptive arm (SelK2 and enoxaparin) and enoxaparin only arms will be calculated and non-inferiority will be concluded if the upper limit of the 90% CI is $\leq 15\%$. Absolute changes from baseline in levels of high-sensitivity CRP and D-dimer will be assessed. A number of secondary analyses may be conducted to assess the robustness of the primary analysis finding.

SelK2 concentrations will be summarized by descriptive statistics.

Safety will be assessed by reported adverse events, changes from baseline during treatment in vital signs, ECGs, laboratory parameters, and physical examination and will be summarized using descriptive statistics. Adverse events will be coded using the (Medical Dictionary for Regulatory Activities) MedDRA dictionary and summarized by system organ class, preferred term, Investigator causality assessment, and treatment group. Incidence of bleeding events (as adjudicated by CIAC) will be tabulated by treatment group.

Sample Size Considerations:

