Assuming that the rate of VTE for the active comparator (enoxaparin) arm of this study will be 25%, it is estimated that a sample size of 76 evaluable patients per arm should give the study 80% power of declaring non-inferiority between the SelK2 only arm and the enoxaparin active comparator arm. This calculation uses a one-sided 90% CI with a non-inferiority margin of 15%. This calculation assumes that the underlying rate of VTE for the SelK2 and enoxaparin arms will be identical at 25% and with the non-inferiority margin set as the midpoint between the expected active therapy response compared with an assumed placebo event rate in this patient population of 55%. Consequently, making the conservative estimate that up to 20% of randomized patients may not have evaluable endpoint data; a total of 95 patients will be enrolled per arm to provide at least 76 endpoint evaluable patients per arm.

Sample Size Considerations for Adaptive Arm:

With the same assumptions as above for the active comparator (enoxaparin) arm of the study event rate, it is estimated that a sample size of 76 evaluable patients in a combination therapy arm of SelK2 and enoxaparin should give the study 80% power of declaring superiority between the SelK2 and enoxaparin and the enoxaparin active comparator arm for an estimated SelK2 and enoxaparin VTE event rate of 6% (a 19% difference between combination treatment effect and active comparator treatment effect). This calculation assumed a two-sided 0.1 alpha, a Pearson Chi-squared test, and a superiority comparison.

TABLE OF CONTENTS

PROTOCOL SYNOPSIS	iii
1.0 INTRODUCTION	1
1.1 Background	1
1.2 Preclinical Studies Supporting SelK2 Antithrombotic Activity	2
1.2.1 In Vivo Mechanism of Action	2
1.2.2 Toxicology	2
1.2.3 Absorption, Distribution, Metabolism, and Excretion	3
1.3 Clinical Studies of SelK2.....	4
1.4 Study Rationale	7
1.5 Rationale for the Dose Regimen	7
2.0 STUDY OBJECTIVES	8
3.0 STUDY DESIGN	9
3.1 Basic Design Characteristics.....	9
3.2 Number of Patients.....	9
3.3 Study Population	10
3.4 Study Phases.....	10
3.4.1 Screening Phase	10
3.4.2 Treatment Phase.....	10
3.4.3 Follow-Up Phase	11
3.4.4 Study Diagrams for SelK2 and Enoxaparin Arms	11
3.5 Efficacy and Safety Assessments.....	12
3.6 Endpoints	13
3.6.1 Primary Efficacy Endpoint.....	13
3.6.2 Exploratory Efficacy Endpoints	13
3.6.3 Pharmacokinetic Assessments of SelK2	13
3.6.4 Pharmacodynamic Assessments of SelK2	14
3.6.5 Safety Endpoints	14

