10.0 STATISTICAL METHODS AND PLANNED ANALYSES

10.1 Sample Size and Power

Assuming that the rate of VTE for the active comparator (enoxaparin) arm of this study will be 25%, it is estimated that a sample size of 76 evaluable patients per arm should give the study 80% power of declaring non-inferiority between the SelK2 arm and the enoxaparin active comparator arm. This calculation uses a one-sided 90% CI with a non-inferiority margin of 15%. This calculation assumes that the underlying rate of VTE for the SelK2 and enoxaparin arms will be identical at 25% and with the non-inferiority margin set as at the midpoint between the expected active therapy response compared to an assumed placebo event rate in this patient population of 55%. Consequently, making the conservative estimate that up to 20% of randomized patients may not yield evaluable endpoint data, a total of 95 patients will be enrolled per arm to provide at least 76 endpoint evaluable patients per arm.

Sample Size Considerations for Adaptive Arm:

With the same assumptions as above the for active comparator (enoxaparin) arm of the study event rate, it is estimated that a sample size of 76 evaluable patients in a combination therapy arm of SelK2 and enoxaparin should give the study 80% power of declaring superiority between the SelK2 and enoxaparin arm and the enoxaparin active comparator arm for an estimated SelK2 and enoxaparin VTE event rate of 6% (an 19% difference between combination treatment effect and active comparator treatment effect). This calculation assumes a two-sided 0.1 alpha, a Pearson Chi-squared test, and a superiority comparison.

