10.3 Statistical Analysis

10.3.1 General Considerations

Descriptive summary statistics include mean, median, standard deviation, interquartile range, and range (minimum, maximum) for continuous variables, and counts and percentages for categorical

variables. Unless otherwise specified, continuous variables will be analyzed using two-sample t-test or Wilcoxon-Mann-Whitney test, whichever is appropriate; and categorical variables will be analyzed using chi-squared test or Fisher's exact test, whichever is appropriate.

SAS 9.3 or later will be used to perform statistical analysis. Unless otherwise specified, a two-sided p-value less than 0.05 will be considered statistically significant. No multiplicity adjustment will be made.

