10.3.3 Efficacy Analyses

For all efficacy analyses, the main analysis will be based on the mITT population. Both primary and secondary endpoint analyses will also be performed on the PP population; these analyses will be supportive only. Comparisons will be made between the SelK2 treated patients SelK2 and enoxaparin treated patients, and the enoxaparin group. The difference of the total VTE rate during the Treatment Phase (from time of randomization up until the day of completion of venogram) between the SelK2, SelK2 and enoxaparin, and enoxaparin treatment groups will be estimated. The lower 1-sided 90% CI of the difference will be calculated and non-inferiority will be concluded if the upper limit of the 90% CI is $\leq 15\%$. The same analysis will be completed on the PP population.

The following secondary analyses will be performed on the mITT and PP populations:

- Comparison of the rates of the individual components of the primary efficacy outcome between the SelK2, SelK2 and enoxaparin, and enoxaparin treatment groups through Treatment Period.
- Conduct primary efficacy analysis of the total VTE rate between the SelK2 treatment, SelK2 and enoxaparin treatment, and enoxaparin treatment with the inclusion of events through Study Day 57.
- Complete comparison of the rates of the individual components of the primary efficacy outcome between the SelK2, SelK2 and enoxaparin, and enoxaparin treatment groups with the inclusion of events through Study Day 57.

Absolute changes from baseline in hsCRP and D-dimer will be summarized by treatment group at each post-baseline visit. Change from baseline in each parameter will be analyzed and compared between treatment groups using a mixed linear model with repeated measures (MMRM).

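### The SelK2-plus-enoxaparin arm is sized for superiority but judged by a 15-point non-inferiority rule that an add-on with no benefit would meet about 80% of the time

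*Combined protocol and SAP*

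**What the plan says.** **Sizing.** The adaptive-arm paragraph of Section 10.1 (repeated in the Synopsis) plans 76 evaluable combination patients to show superiority over enoxaparin, with VTE rates of 6% and 25%: "This calculation assumes a two-sided 0.1 alpha, a Pearson Chi-squared test, and a superiority comparison".

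**Analysis.** The Synopsis (Statistical Methods) first names SelK2 alone versus enoxaparin, then adds that "the difference between the adaptive arm (SelK2 and enoxaparin) and enoxaparin only arms will be calculated and non-inferiority will be concluded" when the upper limit is at most 15%. Section 10.3.3 says the difference in total VTE rate "between the SelK2, SelK2 and enoxaparin, and enoxaparin treatment groups will be estimated", and continues: "The lower 1-sided 90% CI of the difference will be calculated and non-inferiority will be concluded if the upper limit of the 90% CI is" at most 15%. The modification list at the end of the protocol records the three-arm comparison as a deliberate clarification to these two places.

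**Margin.** The Synopsis sizing text for SelK2 alone states "This calculation uses a one-sided 90% CI with a non-inferiority margin of 15" percent. It sets the margin at the midpoint between the expected 25% on active therapy and an assumed 55% on placebo.

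**Default test level.** Section 10.3.1 states that, unless otherwise specified, "a two-sided p-value less than 0.05 will be considered statistically significant".

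**The concern.** The adaptive-arm objective is to assess SelK2 given in addition to enoxaparin, and Sections 1.4 and 10.5 tie activation of the arm to a possible additive effect on VTE. An add-on has to beat its backbone. A rule that is met when the combination may be somewhat worse than enoxaparin alone cannot show this.

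The margin does not carry over either. Fifteen points keeps half of enoxaparin's assumed 30-point advantage over placebo when SelK2 replaces enoxaparin. In the add-on comparison nobody gives up enoxaparin, so there is no enoxaparin effect to preserve.

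The superiority test used for sizing is absent from Section 10.3.3. If one were added later, it would be open to argument whether alpha is the 0.10 of Section 10.1 or the 0.05 default of Section 10.3.1. Followed as written, the primary efficacy comparison can meet its criterion when SelK2 adds nothing or makes VTE worse, and the question that justifies the arm goes unanswered.

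**Working it through.** **Inputs.** From Section 10.1 and the Synopsis: 76 evaluable per arm, 25% VTE on enoxaparin, margin 0.15, one-sided 90% limit (z = 1.2816), 80% power (z = 0.8416). For the combination: 6% versus 25%, two-sided alpha 0.10 (z = 1.645).

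**1. The plan's own non-inferiority figure.** The plan assumes that "the underlying rate of VTE for the SelK2 and enoxaparin arms will be identical at 25" percent.

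n = (1.2816 + 0.8416)² × (0.25×0.75 + 0.25×0.75) / 0.15² = 4.508 × 0.375 / 0.0225 = 75.1, so 76 per arm. Then 76 / 0.8 = 95 enrolled. Both match the protocol.

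**2. The same rule applied to an add-on with no benefit.** Equal rates of 25% are exactly the sizing scenario, so the chance of meeting the rule equals the planned power.

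SE = √(0.375/76) = 0.0702; P = Φ(0.15/0.0702 − 1.2816) = Φ(0.854) = 80.3%.

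**3. Exact probabilities.** Let p be the observed combination rate and q the observed enoxaparin rate. Sum the two binomial distributions (76, 76) over all outcomes that meet each criterion:

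- written rule: p − q + 1.2816 × √[p(1−p)/76 + q(1−q)/76] ≤ 0.15;
- superiority test of Section 10.1, in the direction of benefit: (q − p) / √[p̄(1−p̄) × 2/76] ≥ 1.645, where p̄ is the pooled rate.

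| True combination rate (enoxaparin 25%) | Meets written rule | Superiority test positive |
|---|---|---|
| 25% (no benefit) | 80.6% | 4.9% |
| 30% (5 points worse) | 54.6% | 1.0% |
| 33% (8 points worse) | 37.7% | 0.3% |
| 40% (15 points worse) | 9.9% | not computed |

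**4. One possible result.** Suppose 23/76 (30.3%) have VTE on the combination and 19/76 (25.0%) on enoxaparin. The difference is 0.0526 and SE = √[(0.3026×0.6974 + 0.25×0.75)/76] = 0.0724. The upper limit is 0.0526 + 1.2816 × 0.0724 = 0.145, so the combination is declared non-inferior with a VTE rate 5.3 points higher.

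**5. Other readings, no-benefit case (25% versus 25%, exact).** The text mentions both a lower one-sided interval and an upper limit of the 90% CI, and it does not say whether enoxaparin patients enrolled before activation count as controls. The 38 concurrent controls below are an assumption: half of 76, from the 2:1 allocation.

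| Reading | Meets written rule |
|---|---|
| 95 vs 95 (every endpoint evaluable), one-sided 90% | 86.7% |
| 76 vs 76, one-sided 90% | 80.6% |
| 76 vs 38 concurrent controls, one-sided 90% | 69.5% |
| 76 vs 76, two-sided 90% CI | 69.3% |
| 76 vs 38, two-sided 90% CI | 54.6% |

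**6. Power if the superiority test is used.** For 6% versus 25%, normal-approximation power at 76 vs 76 is Φ{[0.19√76 − 1.645√(2×0.155×0.845)] / √(0.06×0.94 + 0.25×0.75)} = Φ(1.65) = 95.0% (exact 96.4%). With 76 vs 38 it is 86.3% (exact 88.6%). The 80% stated in Section 10.1 does not reproduce at 76 vs 76. That is a separate matter, but it means the superiority test needs no extra patients under either control set.

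**The case against.** The strongest reply is that concluding non-inferiority is not the same as claiming that SelK2 helps. The protocol never calls a non-inferior combination a success, and the only inferential aim stated for that arm, in Section 10.1, is superiority. That is fair as to wording: the 80% is the chance of meeting the written criterion, not of being shown superior. But it is the only criterion written for the comparison, and the Synopsis places it under the primary efficacy comparison. A sizing assumption does not replace an analysis rule.

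Second, the rule is not as lax as the margin suggests, because it bounds a confidence limit. A combination truly 15 points worse passes only about 10% of the time. This stands, but at 5 points worse it still passes more often than not.

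Third, 80% is one reading. This also stands, and the range is shown above. Under every reading computed, a no-benefit add-on passes in more than half of trials.

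Fourth, the 0.05 default applies only unless otherwise specified, and Section 10.1 does specify 0.10, so 0.10 can be argued to govern. That is a reason to state it in Section 10.3.3. The practical effect is modest: normal-approximation power at 76 vs 76 is 95.0% at 0.10 and 90.7% at 0.05.

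Finally, the arm is conditional and this is Phase 2. However, Section 1.4 says the data will support a claim of efficacy and safety, and the rule has to be settled before a committee that includes the sponsor acts on unblinded results.

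**Conclusion.** The concern holds. The sizing text and the analysis text for the combination arm contradict each other, and the analysis text applies a margin that has no basis when both arms receive enoxaparin. At 76 evaluable per arm, 25% VTE on enoxaparin and a Wald one-sided 90% limit, a combination with no benefit meets the written criterion 81% of the time, against 4.9% under the superiority test the arm was sized for. The 81% assumes that enoxaparin patients from before activation are pooled to reach 76. Across the other readings of the interval and control group the figure runs from 55% to 87%. This must be corrected, because it decides what the trial can conclude about the add-on.

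**What to change.** In the Synopsis (Statistical Methods) and Section 10.3.3:

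- Restrict the 15-point non-inferiority rule to SelK2 alone versus enoxaparin.
- For SelK2 plus enoxaparin versus enoxaparin, state the test from Section 10.1: superiority, Pearson chi-squared, two-sided alpha 0.10, reported with the risk difference and its two-sided 90% CI. Say that this overrides the 0.05 default of Section 10.3.1.
- State whether the control group is all enoxaparin patients or only those randomized after activation.
- In the non-inferiority sentence, name the bound as the one-sided 90% upper confidence limit, which is the upper end of a two-sided 80% CI. This matches the sizing. Reading it as a two-sided 90% CI would cut power at 76 per arm from 80% to 69%, and 104 per arm would be needed: (1.645 + 0.8416)² × 0.375 / 0.0225 = 103.04.

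The cost is wording only, with no added patients and no new data. It does need a protocol amendment under Section 12.5, ideally before the adaptive arm is activated.

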MedDRA	Medical Dictionary for Regulatory Activities
PAHA	Primate Anti-Human Antibodies
PD	Pharmacodynamics
PE	Pulmonary Embolism
PK	Pharmacokinetics
PP	Per-Protocol
PSGL-1	P-Selectin Glycoprotein Ligand-1
PT	Prothrombin Time
QTcB	Bazett's corrected QT interval
QTcF	Fridericia's corrected QT interval
RBC	Red Blood Cell
SAE	Serious Adverse Event
SAP	Statistical Analysis Plan
SD	Standard Deviation
SRM	Study Reference Manual
$t_{1/2}$	Terminal Phase Half-Life
TEAE	Treatment-Emergent Adverse Event
TKA	Total Knee Arthroplasty (Total Knee Replacement Surgery)
UA	Urinalysis
VCAM	Vascular Cell Adhesion Molecule
V	Volume of Distribution
VTE	Venous Thromboembolism
V/V	Volume to Volume Ratio
WBC	White Blood Cell
WHO-DD	World Health Organization Drug Dictionary

1.0 INTRODUCTION

1.1 Background

Deep vein thrombosis and pulmonary embolism are collectively referred to as venous thromboembolism (VTE). Venous thromboembolism is a major medical burden affecting millions of people around the world, with approximately 300,000 deaths and 540,000 deaths annually in the United States and the European Union, respectively. Current therapies available for venous thromboembolism include low-molecular-weight heparins (e.g., enoxaparin sodium), vitamin K antagonists (e.g., warfarin), and newer oral anticoagulants (e.g., rivaroxaban; a factor Xa inhibitor). These therapies target the coagulation system and can therefore result in the feared complication of hemorrhage, which can sometimes be fatal.

VTE is one of the most serious complications experienced by patients undergoing joint replacement surgeries such as total knee arthroplasty (TKA). Following elective TKA, objective venographic evidence of primarily asymptomatic deep vein thrombosis (DVT) occurs in 41-85% of patients without thromboprophylaxis. Because of the strong concordance between asymptomatic DVT detected by venography and clinically important VTE, DVT detected by contrast venography is most often used in the early investigation of new antithrombotic agents (1).

Considering the high incidence of VTE following TKA, the use of routine thromboprophylaxis is recommended in these patients. However, agents available for use in this patient population block the coagulation system and can cause major bleeding events leading to significant morbidity and mortality. There is a continuing medical need for the development of novel antithrombotic agents, especially those that may operate through a unique mechanism of action which is not associated with an increase in bleeding risk.

The relationship between VTE and vein wall inflammation has been well established. PSGL-1 (P-selectin glycoprotein ligand-1) and the selectin family of molecules (P-, E- and L-selectin) are cell adhesion molecules, regulating the interactions between leukocytes, the blood vessel wall, and activated platelets. The importance of PSGL-1/selectin interactions in the inflammatory process leading to VTE has been confirmed in several nonhuman primate studies. Collectively, these studies indicate that inhibition of PSGL-1 interactions with its selectin ligands results in a decrease in thrombosis, and importantly, in the absence of bleeding complications. The level of reduction in thrombosis resulting from PSGL-1/selectin inhibition is similar to that with the low-molecular-weight-heparin, enoxaparin, which is associated with bleeding complications.

During total hip and total knee replacement surgeries, endothelium injury and platelet activation result in the upregulation of selectins and disruption of the regulatory mechanisms of hemostasis. Platelets and the endothelium then participate in the formation of blood clots through receptor interactions with PSGL-1 found on multiple inflammatory cell types. The use of a tourniquet in total knee replacement surgery and immobilization following surgery also induces inflammation and increases the risk of thrombosis.

SelK2 is a humanized monoclonal antibody that binds PSGL-1 with high affinity and specificity and blocks its ability to interact with selectins as well as with chemokines. Because of its ability to block the interactions of PSGL-1 with selectins and chemokines, SelK2 may be useful in the prevention of VTE in patients undergoing TKA.

1.2 Preclinical Studies Supporting SelK2 Antithrombotic Activity

1.2.1 *In Vivo* Mechanism of Action

The vascular anatomy and coagulation system of baboons are similar to those of humans. Therefore, baboon models of VTE and bleeding provide an excellent reflection of what might happen in humans. In one such model of DVT, baboons are subjected to either infrarenal inferior vena cava or iliac vein balloon occlusion with hypogastric vein ligation. In a meta-analysis of five different baboon studies using this model, PSGL-1/selectin inhibition reduced thrombosis to a similar degree as enoxaparin (2). Selectin blockade also successfully reduced vein wall inflammation and fibrosis which has important implications for the prevention of postthrombotic syndrome. Importantly, bleeding was not reported in any study and coagulation parameters were not adversely affected.

In a more recent study conducted in a baboon iliac vein stasis model of DVT, a P-selectin binding aptamer that inhibits PSGL-1/P-selectin interactions was shown to be effective in both prophylactic and treatment applications (3). Selectin inhibition resulted in increased iliac vein recanalization and valve competency equal to or greater than those observed with enoxaparin treatment. Importantly, selectin inhibition decreased intimal fibrosis while enoxaparin did not. There were no significant changes in fibrinogen or activated partial thromboplastin time and no bleeding events were observed in the study.

Collectively, these studies indicate that inhibition of PSGL-1 interaction with its selectin ligands results in a decrease in thrombosis and improvements in both valve competency and vessel patency. The reduction in thrombosis with PSGL-1/selectin inhibition is similar to that with enoxaparin. Further, selectin inhibition results in a decrease in vein wall inflammation and fibrosis with no effect on inflammatory cell extravasation into the vein wall. Importantly, the antithrombotic activity with selectin inhibition occurs in the absence of potential bleeding complications characteristic of anticoagulants (4, 5).

These data suggest that the inflammatory and procoagulant factors involved with thrombus initiation and resolution are associated with PSGL-1/selectin interactions on various cell types and that blockade of these interactions may be a novel therapeutic strategy in the prophylaxis and/or treatment of VTE. Further, intervention of the inflammatory response early in thrombogenesis may be beneficial for prevention of postthrombotic syndrome that often develops following DVT.

